9.3.2 Expectedness of SAEs

The NIDCR Medical Monitor and the Study PI will be responsible for determining whether an SAE is expected or unexpected. An adverse event will be considered unexpected if the nature, severity, or frequency of the event is not consistent with the risk information previously described for the intervention.

9.3.3 Severity of Event

The following scale will be used to grade adverse events:

1. Mild: no intervention required; no impact on activities of daily living (ADL)
2. Moderate: minimal, local, or non-invasive intervention indicated; moderate impact on ADL

3. Severe: significant symptoms requiring invasive intervention; subject seeks medical attention, needs major assistance with ADL.

9.4 Reporting Procedures

9.4.1 *Unanticipated Problem Reporting to IRB and NIDCR*

Incidents or events that meet the OHRP criteria for unanticipated problems will be reported to the IRB. Unanticipated problem reports will include:

- appropriate identifying information for the research protocol, such as the title, investigator's name, and the IRB project number;
- a detailed description of the adverse event, incident, experience, or outcome;
- an explanation of the basis for determining that the adverse event, incident, experience, or outcome represents an unanticipated problem;
- a description of any changes to the protocol or other corrective actions that have been taken or are proposed in response to the unanticipated problem

Reporting of Unanticipated Problems to NIDCR is accomplished by submission of an Unanticipated Problem Report via fax or email to Rho Product Safety. Once submitted, Rho Product Safety will send a confirmation email to the investigator within 1 business day.

UP Reporting Contact Information:

- Product Safety Hot Line: [name]
- Product Safety Fax Line: [name]
- Product Safety Email: [contact]

9.4.2 *Serious Adverse Event Reporting to NIDCR*

Any AE meeting the specified Serious Adverse Event criteria will be submitted on an SAE form to NIDCR's centralized safety system via Rho Product Safety. This report may be sent by fax or email. Once submitted, Rho Product Safety will send a confirmation email to the investigator within 1 business day. The investigator should contact Rho Product Safety if this confirmation is not received. This process applies to both initial and follow-up SAE reports.

SAE Reporting Contact Information:

- Product Safety Hot Line: [name] (International: [contact])

- Product Safety Fax Line: [name] (International: [contact])
- Product Safety Email: [contact]

General questions about SAE reporting can be directed to the Rho Product Safety Help Line (available 8:00AM – 5:00PM Eastern Time) at [name] or [contact].

The study PI or Project Manager will complete a Serious Adverse Event Form within the following timelines:

- All deaths and immediately life-threatening events, whether related or unrelated, will be recorded on the Serious Adverse Event Form and sent by fax or email within 24 hours of site awareness.
- Serious adverse events other than death and immediately life-threatening events, regardless of relationship, will be reported by fax or email within 72 hours of site awareness.

Other supporting documentation of the event may be requested by the pharmacovigilance contractor and should be provided as soon as possible.

All SAEs will be followed until satisfactory resolution or until the PI or Sub-investigator deems the event to be chronic or the patient to be stable

9.5 Halting Rules

Study halting may occur as required by the IRB, NIDCR, or DSMB. The study PI may temporarily suspend enrollment pending review by these authorities if warranted based on the presence, type, or frequency of SAE's or other changes in the study protocol which may place participants at greater than anticipated risk.

10 STUDY OVERSIGHT

A Data and Safety Monitoring Board (DSMB) will be convened to periodically review and evaluate the accumulated study data for participant safety, study conduct and progress. Efficacy will not be explicitly monitored as it will not be possible to assess the intervention's efficacy in a meaningful way based on an incomplete sample and the study's low risk level. The DSMB will also make recommendations to NIDCR concerning the continuation, modification, or termination of the study.

The Board will consist of 6 voting members chosen by NIDCR for their expertise in tobacco cessation treatment, quitline counseling, oral health, or biostatistics. The NIDCR Medical Monitor will be a blinded, non-voting member of the Board. The Board will meet at least once a year while the study is actively recruiting or providing intervention to participants, but may meet more frequently as deemed necessary by the Board members. The DSMB will operate under the rules of an NIDCR-approved charter that will be written at the organizational meeting of the DSMB. At this time, each data element that the DSMB needs to assess will be clearly defined. The DSMB will advise NIDCR of its findings. Reports will also be shared annually with the IRB as required.

Confidentiality will be maintained during all phases of the DSMB review and deliberations. Only voting members will have access to interim analyses of outcome data identified by treatment group, except as noted or required by the DSMB.

All DSMB activities will be in compliance with NIDCR guidelines at note at <http://www.nidcr.nih.gov/Research/ToolsforResearchers/Toolkit/DSMBGuidelines.htm>.

11 CLINICAL SITE MONITORING

Clinical site monitoring will not be done for this study; however, the NIDCR reserves the right to conduct independent audits or clinical monitoring as necessary.

12 STATISTICAL CONSIDERATIONS

12.1 Study Hypotheses

All hypotheses tested will be evaluations of superiority of the enhanced intervention (UC cessation counseling + oral health promotion program) compared to UC (UC cessation counseling). Null hypotheses assume that participants in the enhanced intervention group are equal to the participants in the UC group. We hypothesize that, compared to people in the UC arm, participants in the enhanced intervention will:

- a. Be more likely to quit smoking as evidenced by 7 day PPA rates at 6 month follow-up (primary outcome) and at 2 month follow-up (secondary outcome)
- b. Be more likely to see a dental care professional in the past 6 months at 6 month follow-up [primary outcome] or at least be more likely to seek dental care or have scheduled a future appointment [secondary outcome].
- c. Exhibit more positive change in relevant oral health knowledge/beliefs and attitudes (e.g., self-efficacy, motivation) that could influence future behavior change [secondary outcomes].

We hypothesize that positive change in participants' knowledge, attitudes, and beliefs at 2 months will mediate positive change in the primary outcome behaviors at 6 months; and that the Oral Health 4 Life program will be acceptable to quitline callers

12.2 Sample Size Considerations

This is the first study to examine whether an integrated oral health promotion-smoking cessation program delivered through tobacco quitlines will increase abstinence rates, so the potential effect size of the intervention is unknown.

Given this, we have powered the study to detect a 9% increase in abstinence rates between the UC (12%) and enhanced intervention (21%) at 6 months. A difference of

this magnitude (nearly a two-fold increase) would be considered clinically meaningful, but is even more significant when viewed in terms of public health impact (defined as reach x effectiveness)⁴⁶ when the potential reach could be hundreds of thousands of smokers annually. Smaller effects could be statistically significant, but an effect of this size would be an unambiguous indicator that the intervention warrants dissemination. The UC cessation base-rate (12%) is estimated based on the actual end of treatment (~6 months) intent to treat 7-day PPA rates observed in the target quitlines (range =

Table 2. Power Calculations

	Effect Sizes		Sample Size
	Control	Intervention	
Abstinence	12%	20%	880
	12%	21%	712
	12%	22%	590
Dental care	5%	11%	856
	5%	12%	664
	5%	15%	376

All power calculations assume 90% power and use a normal approximation approach with pooled variance.

11% - 12.5%) and is consistent with the estimated abstinence rate of tobacco quitlines based on a meta-analysis of the literature (average cessation rate at 6 months = 12.7% (95% CI, 11.3-14.2)).²³ With a sample of ~712 people, we will have 90% power to detect an 9% difference in rates of smoking abstinence at 6 months assuming a two-sided alpha-level=0.05 Wald Z test statistic for a difference between proportions using a normal approximation with pooled variance⁴⁷ and UC rate of 12%. This sample is also more than sufficient to detect a meaningful difference in the proportion of people who receive dental care (see Table 1). Although no participants will have seen a dentist in the past 6 months at enrollment as a condition of eligibility, it is possible a few will spontaneously seek dental care. Thus, we assume a base rate of 5% for this outcome in the UC group at 6 months. With the proposed sample, we will have >90% power to detect a 10% difference in dental care utilization between groups (e.g., 5% vs. 15%) and greater power to detect larger increases in treatment utilization. Increasing treatment utilization by 10% or more in this high risk population also has public health significance given the potential reach of the program. Each sample size estimate is based on complete case follow-up which will occur by design for all primary outcome analyses since we will be imputing missing values for the primary outcomes (missing cases will be assumed to be smokers and to not have visited the dentist). All analyses assume an intent to treat analysis with all subjects included as randomized. With a sample of n = 718, we also have 80% power to detect a difference of 7.6% in smoking abstinence and 5.6% in dental care utilization.

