Smokers (n ~ 742; minimum of 10 and up to ~30 pilot participants and ~712 main trial participants) will be recruited when they call to enroll in services. Eligible smokers who have not received recent dental care will be randomized to either usual care quitline intervention plus control text messaging or an enhanced program which integrates standard tobacco cessation counseling with a multi-modal, behavioral oral health promotion program. The enhanced program includes behavioral counseling, mailed written materials, access to online materials and resources, support/ outreach via text messaging, and referral information for affordable local dental care. Follow-up assessments will be conducted by phone at 2 and 6 months

post-enrollment. Primary outcomes are: receipt of professional dental care following enrollment [yes/no] and self-reported 7 day point prevalent smoking abstinence at 6 months [yes/no]. We hypothesize that persons who receive the enhanced program will be more likely to see a dentist and to quit smoking.

Secondary outcomes and process measures of interest include: whether a participant either receives professional dental care or has scheduled a future dental appointment at 6 months, smoking abstinence at 2 months, and changes in oral health knowledge and relevant attitudes (self-efficacy, motivation, perceived oral disease severity, and outcome expectations/perceived benefits of oral hygiene) at 2 and 6 months. The incremental cost of delivering the Oral Health 4 Life program will also be examined.

Objectives: Primary Objective: To assess the effects of the proposed behavioral intervention on tobacco abstinence and utilization of professional dental services (primary outcomes).

Secondary Objectives:

- Assess the impacts of the enhanced intervention on key secondary behavioral outcomes and select intermediate outcomes/process measures that could mediate treatment effects.
- Determine the effectiveness of the proposed enhanced intervention, whether it warrants dissemination to smokers through tobacco quitline programs nationally in the current form, or whether further refinement and evaluation are warranted.
- Calculate the incremental cost of adding the Oral Health 4 Life program to usual quitline care and create a decision support tool that quitline sponsors (i.e., potential purchasers of the program) can use to inform decisions about whether to offer the program.

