3 OBJECTIVES

3.1 Study Objectives

The primary objective of this study is to assess the effects of the proposed behavioral intervention on tobacco abstinence and utilization of professional dental services.

The secondary objectives of this study include:

- Assess the impacts of the enhanced intervention on key secondary behavioral outcomes and select intermediate outcomes/process measures that could mediate treatment effects.
- Determine the effectiveness of the proposed enhanced intervention, whether it warrants dissemination to smokers through tobacco quitline programs nationally in the current form, or whether further refinement and evaluation are warranted.
- Calculate the incremental cost of adding the Oral Health 4 Life program to usual quitline care and create a decision support tool that quitline sponsors (i.e., potential purchasers of the program) can use to inform decisions about whether to offer the program.

The results of this project will inform whether the proposed intervention warrants further evaluation or dissemination through tobacco quitlines based on its effectiveness and help purchasers make informed decisions about providing the program.

The intervention will be offered to people seeking treatment for smoking cessation through one of the participating state-funded tobacco quitlines and will reach a high-need, lower-income population who are eligible for these free services.

Additional detail on the proposed enhanced intervention is included in sections 6 and 7.

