3.2.2.2 Cost Analysis Measures and Outcomes

Because the goal of the current study is to assess the degree to which the Oral Health 4 Life program increases the likelihood of both quitting smoking and visiting a dentist and each of these outcomes may be of interest to different purchasers, we will provide a detailed assessment of the costs for each outcome. The analysis will examine the incremental cost of adding the Oral Health 4 Life program to the standard quitline program from the purchaser/payer perspective.

We will assess the estimated additional **cost per counseling call** for which the Oral Health 4 Life program is included and the **cost per successful cessation event**, based on six month outcomes. These calculate these costs we will estimate all resources required to develop and maintain the intervention materials (print and web-based), the increased personnel time to provide oral health counseling, and other outreach services related to Oral Health 4 Life (e.g., text messaging). All associated effort, labor costs, and material costs associated with delivering of the intervention will be tracked at GHRI and Alere.

We will also calculate the **cost per dental visit** attributable to the Oral Health 4 Life program and the **cost per both a successful cessation event and dental visit**, each assessed based on primary 6 month outcomes. The **cost per dental visit** will be assessed as the amount reimbursed by providers for routine preventive office visits. This is appropriate because our analysis takes the payer/provider perspective and while the amount reimbursed per visit is not the cost incurred by the practice it does capture the payer's financial responsibility. We will not include patient incurred costs, whether due to lost productive time or out of pocket expenses, because these costs are not the payer's responsibility. Because we will not have claims data containing details about specific reimbursable services provided at each visit attributable to the Oral Health 4 Life program, we will assign the mean dollar amount dental practices are reimbursed for

preventive visits based on relative resource intensity weights using the American Dental Association's Current Dental Terminology (CDT) coding scheme.

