Mediation Analyses. If the enhanced UC is more effective than UC for either primary outcome at 6 months, we will then conduct mediator analyses to assess whether relevant secondary outcomes measured at 2 months (self-efficacy, motivation, knowledge,) mediate at least part of this effect. Mediation will be explored separately for each significant main outcome. These analyses will be conducted using the framework recommended by Baron and Kenny,⁴⁹ but using more recent statistical methods developed to better quantify and decompose different aspects of the mediation effect.⁵⁰ Having demonstrated the association between the intervention and the outcome variable (the “total effect” of the intervention on the outcome), the second step will be to demonstrate the association between the intervention and each mediator. We will construct a regression model for each mediator with the 2 month score of the mediator as the dependent variable and intervention indicator as independent variables. We will conduct this for each potential mediator and only include those mediators that have at least a $P < 0.10$ -level significant relationship with the intervention as potential mediators in the following step. The third step is to demonstrate the reduction of the intervention effect on the outcome after removing the effect of the mediator(s). We will construct a multi-mediator inverse probability weighted (IPW) regression model. This approach allows us to estimate the direct effect of intervention after rebalancing the intervention groups with respect to the mediators. The application of the IPW approach, as compared to the traditional approach of adjusting for multiple mediators, allows us to more appropriately account for confounding between a mediator and the outcome both

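### Do two primary outcomes, each sized at an unsplit two-sided 5%, need a multiplicity or success rule?

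*Combined protocol and SAP*

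**What the plan says.** The Protocol Summary names two primary outcomes: "Primary outcomes are: receipt of professional dental care following enrollment [yes/no] and self-reported 7 day point prevalent smoking abstinence at 6 months [yes/no"]. Section 12.1 gives each its own hypothesis and states the direction for both: "All hypotheses tested will be evaluations of superiority of the enhanced intervention".

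Section 12.2 gives the significance level once, for abstinence: "assuming a two-sided alpha-level=0.05 Wald Z test statistic for a difference between proportions". The note to Table 2 covers both outcomes but names no level: "All power calculations assume 90% power and use a normal approximation approach with pooled variance". The section closes with figures for 718 participants: "80% power to detect a difference of 7.6% in smoking abstinence and 5.6% in dental care utilization".

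Section 12.4 plans one regression analysis per primary outcome. It sets no significance level, alpha split, test order or multiplicity adjustment, and it does not say that none is needed. Its mediation paragraph opens with the condition "If the enhanced UC is more effective than UC for either primary outcome at 6 months" and then takes each significant outcome separately.

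On what the results are for, section 3.1 says that they will "inform whether the proposed intervention warrants further evaluation or dissemination through tobacco quitlines based on its effectiveness". Section 3.2.2.2 says that the study assesses how far the program "increases the likelihood of both quitting smoking and visiting a dentist and each of these outcomes may be of interest to different purchasers", and it costs each outcome on that ground.

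**The concern.** Two primary tests at full alpha, feeding what reads in section 3.1 as one conclusion about the program, is the usual setting for inflated error. If a significant result on either outcome could be announced as effectiveness of the program, the chance of a false announcement would nearly double when neither behavior is affected.

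The missing success rule matters when exactly one outcome is significant. The rule could then be chosen with the results in hand. The wording leaves room for this: the mediation trigger refers to either outcome, section 3.2.2.2 can be read as aiming at both, and other text treats the two separately.

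**Working it through.** **1. Reproduce the plan's sample sizes.** The inputs are the rates in Table 2, 90% power and 1:1 allocation, with the pooled-variance normal approximation:

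n per arm = [z(1−α/2)·√(2·p̄·q̄) + z(0.90)·√(p1q1 + p2q2)]² / (p2 − p1)²

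For abstinence 12% vs 21% at α = 0.05, p̄ = 0.165:

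(1.960 × 0.5249 + 1.2816 × 0.5211)² / 0.0081 = 355.4, so 356 per arm and 712 in total, as stated.

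| Comparison | Plan | α = 0.05 | α = 0.025 |
|---|---|---|---|
| Abstinence 12% vs 20% | 880 | 880 | 1040 |
| Abstinence 12% vs 21% | 712 | 712 | 840 |
| Abstinence 12% vs 22% | 590 | 590 | 696 |
| Dental 5% vs 11% | 856 | 856 | 1012 |
| Dental 5% vs 12% | 664 | 664 | 784 |
| Dental 5% vs 15% | 376 | 376 | 444 |

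At 718 participants and α = 0.05, power is 79.8% for 12% vs 19.6% and 80.0% for 5% vs 10.6%, which matches the closing figures of section 12.2. Both outcomes were therefore sized at an unsplit two-sided 0.05.

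**2. Error if either outcome were enough.** In the direction of benefit each test has error 0.025. With neither outcome affected and independent tests:

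- benefit on at least one: 1 − (1 − 0.025)² = 4.94%
- either direction: 1 − (1 − 0.05)² = 9.75%

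The documents give no correlation between the two tests, so 0 to 0.5 is assumed and the bivariate normal is used:

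| Correlation | False claim of benefit | Either direction |
|---|---|---|
| 0 | 4.9% | 9.75% |
| 0.3 | 4.8% | 9.5% |
| 0.5 | 4.5% | 9.1% |

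The single-test values are 2.5% and 5%. Counting missing cases as failures on both outcomes induces only a small correlation: 0.02 to 0.15 for an assumed 20-50% shared non-response, if the outcomes are independent among respondents. The figures near 4.9% are therefore the more plausible ones under this reading.

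**3. Does the plan state that reading?**

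- Section 12.1 sets a separate hypothesis for each outcome.
- Section 12.4 fits a model over both follow-ups for abstinence and a single logistic regression for dental care. Mediation is examined outcome by outcome.
- Section 3.2.2.2 and the economic part of section 12.4 give cessation, a dental visit, and the two together their own costs and success probabilities. Purchasers then judge from estimates, confidence intervals and their own willingness to pay.
- Section 3.1 lists the dissemination question as a secondary objective with graded answers: disseminate in the current form, or refine and evaluate further.
- Section 12.2 ties dissemination to a 9-point abstinence effect, and it notes that smaller effects could also reach significance. That criterion is the size of one outcome's effect. It is not p < 0.05 on either outcome.
- The word either appears as a trial-level condition only in the mediation paragraph, where it opens explanatory analyses.

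No section makes significance on either outcome the definition of trial success.

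**4. What an adjustment would cost.** Under Hochberg, both outcomes are significant if both p-values are below 0.05; otherwise the smaller must be below 0.025. At 718 participants with abstinence 12% vs 21%, unadjusted power is 90.3%. Under Hochberg it is:

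- 90.2-90.3% if dental care is 5% vs 15%
- 89.3-89.8% if dental care is 5% vs 12%
- 84.8% if dental care is unaffected

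Reaching 90% for abstinence at 0.025 would take 840 participants (step 1). Section 12.4 reports enrollment complete, with 718 in the primary sample.

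All of these figures use the plan's own z approximation, not the adjusted regression models.

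**The case for a change.** The strongest opposing case is that the plan never adopts the separate-claims reading in so many words, and that a split result is likely. At 718 participants with abstinence 12% vs 21%, exactly one outcome is significant in 9.6-10.1% of trials if dental care is 5% vs 15%, in 12.2-16.1% if it is 5% vs 12%, and in 86-88% if dental care is unaffected. One or two sentences written before the analysis would stop anyone from picking the rule afterwards, and no participants would have to be added.

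The arithmetic stands, and so does the observation that no rule is written. Three things weaken the conclusion.

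- A split result is hard to misreport, because both outcomes are pre-specified as primary and both will be shown. A reader who wants one overall claim can apply 0.025 to the smaller p-value.
- With dental care 5% vs 15%, the roughly 10% of split results are nearly all dental-only (9.4-9.6%). In those trials abstinence is not significant, and the dissemination signal in section 12.2 rests on abstinence.
- The possible rules are incompatible with one another. Two of them, requiring both outcomes or making two separate claims, need no alpha adjustment. Statisticians reasonably disagree about adjusting across distinct outcome-specific claims, so Hochberg here would be a preference with a price in power.

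**Conclusion.** No change follows. The plan is silent on multiplicity, but its structure points to two outcome-specific claims. Analysts following it would test each outcome at two-sided 0.05 and report both, and each claim would keep its own error: 5% two-sided, 2.5% in the direction of benefit.

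The rise to about 4.5-4.9% depends on an either-suffices rule that appears nowhere in the plan, and on an assumed correlation of 0 to 0.5. Guarding against it would lower abstinence power from 90.3% to about 85% if dental care is unaffected. The conclusion assumes that a single significant outcome is reported as a finding on that outcome, as sections 12.1, 12.4 and 3.2.2.2 set things up. A sentence saying so would record what the plan already implies without altering any analysis.
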